9.2.2. Sampling Methods

For **Trifluridine and tipiracil assessment**, 4 mL of blood will be taken at each timepoint ([Appendix 12](#)). Concentrations of trifluridine and tipiracil will be determined in sodium heparinised plasma, using a mass spectrometry, validated according to current regulatory guidelines.

For **Futuximab and modotuximab assessment**, 2.5 mL of blood will be taken at each timepoint ([Appendix 12](#)). Futuximab/modotuximab will be determined in serum, using an enzyme-linked immunosorbant assay, and validated according to current regulatory guidelines.

Preparation and management of the bioanalytical samples will be described in a separate document.

9.3. Pharmacodynamic measurements

Not applicable.

9.4. Assessment of biomarkers

While the goal of the biomarker assessments is to provide supportive data for the clinical study, there may be circumstances when a decision is made to stop a sampling collection, or not perform or discontinue an analysis due to either practical or strategic reasons (e.g. inadequate sample number, issues related to the quality of the sample or issues related to the assay that preclude analysis, impossibility to perform correlative analyses, etc.). Therefore, depending on the results obtained during the study, sample collection analysis may be omitted at the discretion of the sponsor.

Peripheral whole blood (20 mL) will be collected pre-dose on C1D1, C2D1, C3D1 then every 2 cycles along with tumour assessment and at withdrawal visit, and analysed centrally for ctDNA monitoring. Potential predictors of response as well as mechanisms of resistance could be explored. The collection is mandatory for all participants. Backup DNA extracts will be stored, with the consent of the participant, for a maximum of 25 years after the end of the study according to local regulation for retrospective analysis restricted to the study of the pathology and the response to the treatment. All samples may be destroyed at any time on participant's or sponsor's request.

Additional details and the sample collection instructions are provided in laboratory manual.

9.4.1. Mandatory assessment

Participation in the study implies a systematic participation in the mandatory investigation. All participants will have to consent to this investigation by signing the main information and consent form for participation in the study. In addition, in case of consent withdrawal, related samples will be destroyed after mandatory assessment is completed and in any case before the clinical study report final version is made available.

Overall results of the genomics biomarkers assessment may be transmitted to the participant upon his/her request through the investigator, according to local regulations if applicable.

9.4.1.1. Sampling, processing and storage

In all participants, 20 mL of blood will be taken at each timepoint.

The plasma will be separated by centrifugation and stored at < -70°C in appropriate labelled storage cryotubes and sent on dry ice. DNA will be extracted from plasma sample and subjected to genomic analysis for circulating tumour DNA monitoring. Preparation and management of the samples will be described in a separate document.

These samples are dedicated to retrospective analysis if participants consent and will be destroyed at the end of the storage period. If participants withdrawn his/her Informed consent form, please refer to [Section 9.4.1](#).

Table (9.4.1.1) 1 - Biomarker(s) experimental conditions

Biomarker(s) assessed	Experimental conditions		
	Sampling time points	Matrix	Purpose
Circulating tumour DNA	C1D1, C2D1, C3D1 CxD1 (every 2 cycles) Withdrawal visit	Blood	ctDNA monitoring

9.4.1.2. Labelling and transfer to analytical centre

Samples will be single coded with a unique number and thus will not carry any personal identifiers.

Samples collection information must be entered as required on the appropriate sample collection e-CRF page(s) and requisition form(s).

Detailed instructions for the samples labelling and shipments are outlined in the laboratory manual (or equivalent) for the study.

The randomisation list will be sent to the analytical centre in order to select the samples to be analysed.

9.4.1.3. Transfer of analytical results

Final analytical results will be transferred to Data Management according to [Section 14.2](#).

9.4.2. Retrospective analysis

Retrospective analyses involving human biological samples are considered as **optional** assessments and are performed after the end of the study (planned or not in the clinical study protocol).

Participation in these retrospective analyses is optional and is not mandatory for the inclusion of a given participant in the study.

If the participant agrees, some additional samples / remaining biomarker samples may be stored after the end of the study.

They could be further analysed to address scientific questions related to the product or disease including research related to improvements or enhancements in the development of bioanalytical methods.

A decision to perform such exploratory biomarker research studies will be based on outcome data from this study or from new scientific findings related to the drug class or disease, as well as reagent and assay availability.

Samples will be kept in suitable conditions in a central bio-repository specialized in storage of biological samples until further notification from the sponsor and may be retained stored up to 25 years after study closure completion.

9.4.3. Transfer of pharmacogenomics results

If the analysis is required during the study, final analytical results will be transferred to Data Management at the end of the study.

9.4.4. Interpretation

If relevant for the project, an evaluation will be carried out and reported in a separate document. This evaluation will be performed by analysing the associations between polymorphisms in relevant absorption, distribution, metabolism, and excretion (ADME) genes and the pharmacokinetics of futuximab/modotuximab.

9.5. Immunogenicity

Blood samples (2.5 mL) for the evaluation of immunogenicity will be collected at the timepoints listed in Table (9.5) 1. The accurate sampling dates and times must be recorded in the e-CRF.

Table (9.5) 1 - Sample Collection Timepoints for futuximab/modotuximab (during the Safety Lead-In and Arm A of Randomised part)

Futuximab/modotuximab assessment	
C1D1	Pre-dose*
C1D15	Pre-dose*
C2D1	Pre-dose*
C2D15	Pre-dose*
CXD1	Pre-dose* ^{**}
WV	During the visit

*i.e. 5-60 minutes before infusion of futuximab/modotuximab

**The frequency of futuximab/modotuximab immunogenicity assessments will be reduced to every 2 months after the first 6 months in the first year and every 4 months after the first year.

In all participants, 2.5 mL of blood will be taken at each timepoint ([Appendix 12](#)). ADA will be determined in serum, using an Immunoassay method, validated according to current regulatory guidelines.

ADA Backup samples will be stored, for a maximum of 3 years after the end of the study, to allow additional analyses related to immunogenicity assessment to be performed in case of agencies' request during their review process. All samples will be destroyed at the latest at the end of the storage period or at any time on participant's or sponsor's request.

9.6. Quality of Life Assessments (Only for Randomised part)

EORTC Quality of Life Questionnaire - Core Questionnaire (EORTC QLQ-C30) ([Appendix 6](#)) and EQ-5D-5L ([Appendix 5](#)) will be completed by the participant on an e-PRO, independently of the study personnel at the following time points, at the beginning of each visit at the following time point:

- Inclusion.
- After the end of cycle 1 (C2D1)
- Every 2 cycles during the treatment period (C3D1, C5D1...).
- WV.
- Every 2 months during the follow-up period, until death or until end of the study is reached (whichever occur first).

Participants will be provided with specific instructions in order to be comfortable with the e-PRO device and enhance the quality of the data. In case the participant is not able to use e-PRO, a caregiver (not a medical/investigator staff) will be allowed to read the questions to the

participant and to collect the answer without any interpretation of the questions and the answers. Data entered by the participant will be sent to a central database via a secured transfer.

10. STATISTICS

10.1. Statistical analysis

A Statistical Analysis Plan (SAP), and associated templates for Tables, Listings and Graphs, will be written and completed before database lock. These specifications will detail the implementation of all the planned statistical analyses in accordance with the main characteristics stated in the protocol.

10.1.1. Analysis sets / Treatment groups

10.1.1.1. Analysis sets

Full Analysis Set (FAS): In accordance with the ITT principle and [Section 5.2.1](#) of ICH E9 guideline,³⁹ all participants to whom a therapeutic unit was randomly assigned using IWRS. Participants in the FAS will be analysed in the arm they were assigned by randomisation. FAS will be used in all efficacy analyses of Randomised part, unless otherwise specified.

Safety Set (SS): All participants having taken at least one dose of IMPs. Participants will be analysed according to the treatment actually received. SS will be used in all analyses of Safety Lead-In part and safety analyses of Phase 3 part.

Per-Protocol Set (PPS): all participants in the FAS who do not violate the terms of the protocol in a way that would affect the study outcome significantly. Participants not fulfilling one of the following criteria will not be included in the PPS:

- Must have histologically or cytologically confirmed adenocarcinoma of mCRC [Screening criterion #2].
- Should be without RAS (KRAS and NRAS) mutations and without BRAF mutation [Screening criterion #3].
- Must have received at least 2 prior regimens of standard chemotherapy for mCRC and had demonstrated progressive disease or intolerance to their last regimen [Screening criterion #5].
- Should have received previous treatment with commercially available anti-EGFR mAbs for ≥ 16 weeks [Screening criterion #6].
- ECOG performance status 0 or 1 [Screening criterion #9].
- Currently receiving or having received anticancer therapies within 4 weeks prior to first IMP administration [Non-screening criterion #14].

PRO Analysis Set: All participants from the FAS who have completed screening and at least one post baseline assessment. Quality of life (QoL) endpoints will be evaluated on PRO Analysis Set.

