6.1.1.3. Schedule

- Once weekly on Day 1, Day 8, Day 15, and Day 22 (\pm 2 days) of each cycle (4 weeks [28 days] equals 1 dosing cycle).

A weekly dosing schedule is to be maintained, unless delay is required to allow for amelioration of toxicities (or in the event of scheduling difficulties associated with extended weekends, holidays, etc.). Futuximab/modotuximab should be administered after trifluridine/tipiracil intake.

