10.1.2.5.1. Analysis

10.1.2.5.1.1. EORTC QLQ-C30

The raw QoL data will be scored according to the EORTC scoring manual and the change in score from baseline in the global health status (GHS) scale is identified as the primary QoL variable of interest.

The completion and compliance rates will be summarised by treatment group for each scheduled assessment timepoints.

The completion rate is defined as the rate of participants who completed the QoL instrument among participants in the QoL analysis set.

The compliance rate is defined as the rate of participants who completed the QoL instrument among participants still on treatment at each visit.

Baseline values and changes in scores from baseline (GHS and each sub-scale score) will be summarized at each scheduled assessment time point descriptively.

A repeated-measures mixed-effects model (SAS PROC MIXED) that includes terms for treatment arms, baseline stratification factors, baseline sub-scale score and time of visit will be used to compare the two treatment groups with respect to changes from baseline in the GHS and each sub-scale score longitudinally over time.

Time to definitive ≥ 10 points deterioration from baseline in the GHS and in each sub-scale, will be compared between the two treatment arms in the QoL analysis set using the stratified log-rank test at a 2-sided 5% level of significance (strata based on IWRS data). Death will be considered to be a deterioration event of QoL. Participants receiving any further anti-neoplastic therapy before definitive worsening will be censored at the date of their last QoL assessment before starting this therapy. Participants who have not worsened as of the cut-off date for the analysis will be censored at the date of their last assessment (questionnaire) before the cut-off. Participants without evaluable questionnaire at baseline will be censored at their randomisation date + 1 day. The distributions will be described using Kaplan-Meier curves including the median time to definitive 10 points deterioration.

10.1.2.5.1.2. EORTC EQ-5D-5L

The dimensional 5-level system will be converted into a single index utility score: the utility index will be derived according to specific country algorithms.

The completion and compliance rates will be summarised by treatment group for each scheduled assessment timepoints.

The completion rate is defined as the rate of participants with evaluable EQ-5D-5L assessment among participants of the EQ-5D-5L analysis set.

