10.2. Determination of sample size

Approximately 25 participants will be evaluated in Safety Lead-In part. The DMC will initially determine tolerability after 6 evaluable participants have been treated. If ≤ 2 participants out of the first 6 experience a DLT, and the DMC based on the totality of safety data determines the doses to be tolerable, then the Safety Lead-In will be expanded by an additional cohort of 6 participants. The DMC will again assess the tolerability when 12 participants have been enrolled and the 12th participant has completed the first treatment cycle. If ≤ 3 participants experience a DLT, and the DMC based on the totality of safety data determines the doses to be tolerable, the Safety Lead-In will be expanded to add another 13 participants, for a total of 25 participants. The DMC will meet again at the end of the Safety Lead-In part when approximately 25 participants have been treated.

The primary endpoint of Randomised part will be OS in DN population, the key secondary endpoint will be OS in TN population. The primary hypothesis will test whether treatment with trifluridine/tipiracil in combination with futuximab/modotuximab compared with trifluridine/tipiracil alone leads to OS prolongation in DN population. A total of 500 patients will be randomised in a 1:1 ratio to the 2 treatment arms and followed-up until at least 383 OS events are observed across the 2 treatment arms will provide 90% power to detect a true hazard ratio (HR) ≤ 0.71 (median OS: 8.5 *vs* 12 months) using a stratified log-rank test (stratified by Performance Status [PS] [0 *vs* 1], extracellular domain EGFR mutations [extracellular domain (ECD)] [presence *vs* absence] and previous regimens of treatment [2 *vs* ≥ 3]), with an overall 1-sided significance level of 0.025 for the primary endpoint (adjusted for OS interim analyses). Assuming enrolment over 21 months with a ramp-up to a maximum of 30 patients per month and a lost-to-follow-up rate of 7% across both treatment arms, the timing of the primary analysis is expected to be at 37.5 months after 1st randomisation.

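### The PRO Analysis Set drops participants who die before any post-baseline questionnaire, although time to definitive deterioration counts death as an event

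*Protocol*

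**What the plan says.** Section 10.1.1.1 of the protocol restricts the PRO Analysis Set to "All participants from the FAS who have completed screening and at least one post baseline assessment" and adds: "Quality of life (QoL) endpoints will be evaluated on PRO Analysis Set".

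Section 10.1.2.5.1.1 (EORTC QLQ-C30) compares the time to a definitive worsening of at least 10 points, for global health status and each sub-scale, "in the QoL analysis set using the stratified log-rank test at a 2-sided 5% level of significance". That set name has no definition of its own. Two rules follow:

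- "Death will be considered to be a deterioration event of QoL".
- "Participants without evaluable questionnaire at baseline will be censored at their randomisation date + 1 day".

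Section 9.6 schedules the questionnaires at inclusion, at C2D1, every second cycle from C3D1, at the withdrawal visit and every two months in follow-up. Section 6.1.1.3 fixes the cycle length: "4 weeks [28 days] equals 1 dosing cycle". The first scheduled post-baseline form therefore falls about 28 days after the first dose.

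The protocol plans no FAS version of this analysis. SAP Version 2.0 states that the Randomised part was cancelled (Section 1) and marks quality of life as not applicable (Section 3.6 and Appendix D).

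**The concern.** The set and the endpoint do not fit each other. The endpoint rules are written for a population that includes people who die early and people without a usable baseline form. The set leaves out anyone with no post-baseline form, and nearly everyone without a baseline form.

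Three consequences follow.

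- A death before any post-baseline form is an event under the endpoint rule but is not in the analysis.
- The same holds for someone who stops early, completes no form, stays in survival follow-up (Section 5.8.2) and later dies without having started further anticancer therapy.
- The rule for a missing baseline form has little left to act on.

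Membership depends on what happens after randomisation, so the comparison loses the protection of randomisation. The trial is open-label and the arms differ in toxicity and in visit burden. Early attrition could therefore differ between them, and an arm with more early deaths would look better on this endpoint than it should.

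**Working it through.** **1. The plan's own figure.** No sample size, event count or power is given for time to deterioration. The nearest design figure is in Section 10.2: 383 OS events, 90% power, hazard ratio 0.71, medians 8.5 and 12 months, one-sided 0.025. Simulating the three OS looks (128, 255 and 383 events) with the boundaries in Table (10.2) 1 gives power of 0.897 at a hazard ratio of 0.71 and 0.900 at 8.5/12 = 0.708. The figure reproduces, so the two medians are a fair basis for the next step.

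**2. Deaths before the first scheduled form.** Inputs: "A total of 500 patients will be randomised in a 1:1 ratio to the 2 treatment arms", so 250 per arm; Day 28; 30.44 days per month (SAP Section 5.1.3). Exponential survival is an assumption. With t = 28/30.44 = 0.92 months and P = 1 − 0.5^(t/median):

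- Control: 1 − 0.5^(0.92/8.5) = 0.072, and 250 × 0.072 ≈ 18.
- Combination: 1 − 0.5^(0.92/12) = 0.052, and 250 × 0.052 ≈ 13.
- Together about 31 of 500, or 6.2%.

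If the first completed form were the one at C3D1 (Day 56), the figures would be 13.9% and 10.1%: about 35 and 25, or 60 of 500.

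**3. Effect on the hazard ratio.** Simulation assumptions:

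- 250 per arm and 1,000 runs per scenario.
- A given share dies before Day 28. After that, death (medians 8.5 and 12 months) and deterioration (median 4 months in both arms) compete as exponential hazards.
- Censoring at 12 months.
- The PRO set omits every death before Day 28.

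The 4-month median and every early-death split other than 7.2%/5.2% are assumptions that the documents do not supply.

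| Early deaths, control / combination | HR, all randomised | HR, PRO set |
|---|---|---|
| 7.2% / 5.2% (protocol medians) | 0.897 | 0.910 |
| 6.2% / 6.2% | 0.911 | 0.906 |
| 5% / 10% | 0.964 | 0.905 |
| 10% / 5% | 0.865 | 0.907 |
| 3% / 12% | 1.007 | 0.904 |
| 12% / 3% | 0.825 | 0.904 |

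The last column hardly moves, and simple arithmetic shows why. After Day 28 the hazard ratio is (1/12 + 1/4)/(1/8.5 + 1/4) = 0.333/0.368 = 0.907 whatever happened earlier. The PRO set cannot register an early-death imbalance. In the 3%/12% case it shows a benefit for the combination that is absent among all randomised participants.

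Under the protocol medians, the set loses about 31 of 468 events, and the median times rise from 3.35 to 3.64 months (control) and from 3.69 to 3.91 months (combination).

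**The case against.** A reader might infer more than the documents support, on four counts.

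- **That early toxicity withdrawals disappear.** They generally do not. Stopping study drug is not leaving the study (Section 5.8.1), a withdrawal visit is offered within four weeks (Section 5.8.2), and forms are due at that visit and throughout follow-up (Section 9.6). Completing any one of them admits the participant. Those lost are people who die, withdraw entirely, are lost to follow-up or never complete a form. Of these, anyone not known to have died would in any case be censored at the last form, here the baseline one, and would add almost nothing to the log-rank test.
- **That the missing-baseline rule can never apply.** The set definition speaks of completed screening, not of an evaluable baseline questionnaire, and the analysis is run scale by scale. A baseline form that is unusable for one scale still triggers the rule. It is largely idle, not void.
- **That bias is demonstrated.** Under the protocol's own medians the shift is negligible. The larger shifts come from assumed splits.
- **That 31 early deaths should be expected.** This is an upper-end count. Eligibility requires a life expectancy of at least 12 weeks and ECOG 0 or 1, both rechecked at randomisation, and a withdrawal-visit form would keep some of those who die early in the set.

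It is also fair to say that quality of life is a secondary endpoint outside the stated error control, which covers OS only, and that Section 10.1 leaves implementation detail to the SAP. The cancelled Randomised part means that this comparison will not be run.

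What survives is the mismatch itself. The protocol states a set and an event rule that disagree about the same participants, and nothing elsewhere resolves it.

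**Conclusion.** The point holds as a defect in the protocol's Randomised-part plan. The analysis set for time to definitive deterioration is conditioned on a post-randomisation event and omits deaths that the endpoint counts.

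The number affected is at most about 18 control and 13 combination participants by Day 28. This assumes exponential survival at the protocol medians and that no early death left a withdrawal-visit form. The expected distortion on those assumptions is about 0.01 on the hazard ratio, given a 4-month median deterioration in both arms. The documents fix neither its size nor its direction. It favours whichever arm has relatively more early deaths, and it matters only if early deaths or drop-outs are unbalanced, which an open-label design with different toxicity profiles makes possible.

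No reported result changes, because SAP Version 2.0 no longer includes the analysis. The correction is worth making in the protocol text, above all if that text is reused.

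**What to change.** - In Section 10.1.2.5.1.1, analyse time to definitive deterioration in the FAS, with the death and missing-baseline rules that the section already gives.
- In the same place, say which rule governs a participant who has no evaluable baseline form and then dies, since in the FAS both would apply.
- In Section 10.1.1.1, limit the post-baseline requirement to the change-from-baseline summaries and the repeated-measures model.
- Use one set name throughout. The QoL analysis set and the EQ-5D-5L analysis set named in Section 10.1.2.5.1 are not defined separately.

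The cost is a sentence or two in each section. No new data are needed, because deaths are already collected for OS.
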